with either an open, laparoscopic, or robot-assisted laparoscopic approach. **The expected enrollment rate is 2 patients/month.**

Patients diagnosed with primary HCC classified as stage 0 (very early) or stage A (early) will be considered for inclusion in this study. Tumors will be staged preoperatively with computed tomography (CT) and/or magnetic resonance imaging (MRI). Laparoscopic ultrasound will be performed intraoperatively.

Eligible patients will meet the following inclusion criteria:

- Male or female patients aged ≥ 18 and ≤ 75 years
- Primary diagnosis of HCC according to the guidelines published by the American Association for the Study of Liver Diseases (AASLD)²⁸ and the diagnostic criteria used by the European Association for the Study of the Liver (EASL)²⁹:
 - Two imaging techniques showing typical features of HCC; or
 - Cytologic/histologic diagnosis of HCC; or
 - Radiographic classification as LIRAD 5 (Appendix III), regardless of AFP level.
- HCC classification of stage 0 (very early) or stage A (early) according to BCLC staging system criteria (Appendix I):
 - Solitary HCC lesion < 3 cm in diameter
 - ≤ 3 HCC lesions, each ≤ 3.0 cm in diameter
- Total bilirubin level, with or without portal hypertension, less than or equal to 3.0.
- Adequate clinical condition to undergo laparoscopic or robot-assisted laparoscopic TAE and/or MWA as treatment for HCC
- Willing and able to give informed consent

Patients meeting the inclusion criteria will be subjected also to the following exclusion criteria:

- Radiologic (CT or MRI) evidence of invasion into major portal/hepatic venous branches and no extrahepatic metastases (LR-5V or LR-M radiologic classifications)
- Evidence of residual disease at first post-MWA CT examination
- Body Mass Index (BMI) > 35
- Previous history of hepatic resections
- Severe renal dysfunction (creatinine clearance of < 40 mL/min)

- Pregnant or nursing women

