According to a computer-generated variable size blocked randomization method, eligible patients will be allocated on a 1:1 basis to receive the experimental therapy (MWA + TAE) and standard therapy (MWA alone), respectively. The nature of the treatments and their possible adverse effects preclude the use of double-blind and double dummy techniques. In patients randomized to receive the experimental therapy, TAE treatments will be initiated within one week of randomization, then followed by MWA within 4 to 6 weeks after reviewing radiological scans from TAE. MWA will be performed 4 to 6 weeks following randomization in MWA standard therapy groups. Treatment may be discontinued if any exclusion criteria develop in the patient or at the patient's request.

Sample Size

Power calculations are based upon expected 2-year survival rates. The main endpoint is 2-year intrahepatic disease-free survival, measured from the time of randomization which is measured from time of randomization and is defined as the absence of local or regional recurrence of HCC as determined by diagnostic imaging. Considering an estimated 80% and 90% intrahepatic disease-free survival at 2 years of follow-up for patients receiving MWA alone and MWA + TAE combination therapy, respectively, a sample size of 92 patients is required to detect a clinically meaningful 10% absolute difference in 2-year peritoneal disease-free survival with MWA + TAE with a minimum of 95% power and a 2-sided $\alpha = .05$. To account for a 5–10% withdrawal rate (following intraoperative detection of vascular invasion or extrahepatic metastasis, etc.), a sample size of 100 patients is required (50 patients per arm). If the rate of patient enrollment is suboptimal, a covariate adaptive randomization method will be used to allocate patients in a 2:1 ratio to receive experimental therapy (MWA + TAE) and standard therapy (MWA alone), respectively, which would result in an overall sample size of 83 patients.

Clinical Procedures

Preprocedural Strategy

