All parameters will be prospectively collected. The study will be approved by the Internal Review Board of Carolinas Medical Center, and informed consent will be obtained from all patients prior to study participation. All hepatocellular carcinomas will be classified according to the TNM criteria of the American Joint Commission on Cancer (AJCC) 2010 Cancer System. A comprehensive medical history will be obtained from each patient and supplemented by clinical notes. Pre-, intra-, and postoperative variables (Table 1) and clinical outcomes will be recorded in an electronic database. Toxicity induced by TAE and or MWA will be graded according to the [Common Terminology Criteria for Adverse Events - CTCAE v5.0](#) (Slated for release in October 2015; v4.3 available at <http://evs.nci.nih.gov/ftp1/CTCAE/About.html>).

Table 1. Variables for analysis

Patient characteristics	age, sex, viral hepatitis status, nicotine use, alcohol use, drug use, hypertension, obesity, diabetes mellitus, general conditions, prior therapy, underlying disease status as determined by Child-Pugh and MELD score
Preoperative imaging	presence of cirrhosis; tumor size, location and number
Intraoperative findings	surgeon performing procedures, proximity of tumor to portal pedicle, number of TAE applications, number of MWA applications, power settings, ablation duration (per application and per tumor), pathology from random liver biopsy
Postoperative data	Tumor radiology, length of stay, 30- and 90-day readmission, wound infection, postoperative complications (encephalopathy, liver failure, ascites, upper GI bleeding), postoperative Δ MELD score
Tumor characteristics	BCLC classification, Okuda stage, AJCC clinical tumor stage, venous infiltration, lymphatic infiltration
Laboratory data	α -fetoprotein (AFP) level, Hb, leukocytes, thrombocytes, serum proteins, albumin, bilirubin, γ -GT, ASAT, creatinine, INR, alkaline phosphatase

Abbreviations: MELD, Model for End-Stage Liver Disease; TAE, transarterial chemoembolization; MWA, microwave ablation; GI, gastrointestinal; BCLC, Barcelona Clinic Liver Cancer; AJCC, American Joint Committee on Cancer; Hb, hemoglobin; γ -GT, gamma-glutamyl transpeptidase; ASAT, aspartate amino transferase; INR, international normalized ratio.

Definitions

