Patients alive at the time of analysis will be censored at the last follow-up examination or at liver transplantation. Univariate analyses will be performed using the log-rank test of equality for categorical variables and the chi-square test with Cox proportional hazard model for continuous variables to identify clinical variables (Child–Pugh class, Okuda class, Model for End-Stage Liver Disease (MELD) score, etiology of cirrhosis), tumor factors (extrahepatic disease, multicentric disease, tumor size, Milan criteria, AJCC tumor stage, AFP level), and treatment-related factors (TAE, complications, recurrence) predicting intrahepatic disease-free and overall survival. Survival and disease-free survival will be estimated using the Kaplan–Meier method and tested with the log-rank test following the intention-to-treat principle. Statistical analysis will be performed using SAS software (SAS Institute, Cary, NC, USA).

The analysis will be planned at a median follow-up of two years, with an interim analysis scheduled for 1 year after the first patient is enrolled or when 50% of total expected enrollment has been reached.

To improve patient selection in the future, additional exploratory analyses will be performed to identify potential prognostic factors. Table 1 details variables that will be included in a Cox proportional hazards regression model to obtain hazard ratios and 95% confidence intervals (CIs). All P values will be two-sided and a p value $< .05$ will be considered significant.

ETHICAL AND SAFETY CONSIDERATIONS

Protection of Patients

The techniques and procedures used in this study protocol are not investigational or provisional in nature; rather, they are established in the provision of care for patients of the HPB Division at Carolinas Medical Center. The therapeutic benefit of combination of TAE/MWA treatment in this patient population remains unknown and is the focus of this study. The additive risk for adverse events is expected to be equal to the individual risks of the study procedures in this protocol.

Standard Division-specific guidelines will be closely followed to ensure patient safety and clinical well-being during all procedures. Patients will be closely monitored for complications associated with MWA and TAE, including wound complications, hematologic toxicities, and others.

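### Read as one model, the exploratory Cox regression would put about 52 Table 1 items on about 14 to 15 recurrences at the planned analysis, too few for usable hazard ratios or confidence intervals

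*Combined protocol and SAP*

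**What the plan says.** The exploratory paragraph under Statistical Analysis announces that "additional exploratory analyses will be performed to identify potential prognostic factors", so that patients can be better selected in future. It continues: "Table 1 details variables that will be included in a Cox proportional hazards regression model to obtain hazard ratios and 95% confidence intervals". It names no endpoint for this model and states no selection rule, cap on terms, penalisation or expected number of events. The section closes by applying a two-sided .05 threshold to all P values. Univariate analyses of intrahepatic disease-free and overall survival are described separately, at the start of the section, on a shorter list of factors.

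The list is under Data Collection: "Table 1. Variables for analysis". It covers patient, imaging, intraoperative, postoperative, tumor and laboratory items.

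Three other statements fix how many events to expect:
- Sample Size: "Considering an estimated 80% and 90% intrahepatic disease-free survival at 2 years of follow-up" for MWA alone and MWA + TAE respectively.
- Patient Eligibility and Allocation: "The expected enrollment rate is 2 patients/month".
- Statistical Analysis: "The analysis will be planned at a median follow-up of two years".

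**The concern.** The information in a Cox model comes from its events, not from its patients. The plan expects few recurrences and lists many covariates. If some combination of covariates orders the events perfectly against the patients still at risk, the partial likelihood has no finite maximum: coefficients drift towards plus or minus infinity, and the usual confidence intervals mean nothing.

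The purpose is to guide future patient selection, so what is at stake is the credibility of whatever prognostic factors are reported. Followed literally, the instruction would produce either a convergence failure or extreme hazard ratios. The likely response, dropping variables until the software converges, would yield a data-driven model presented as a planned one, with P values judged at .05.

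**Working it through.** **The plan's own figure.** The plan states no event count, so there is none to reproduce. Its sample size of 92 for 95% power does not reproduce: [1.96·√(2·0.85·0.15) + 1.645·√(0.8·0.2 + 0.9·0.1)]²/0.1² gives 329 per arm, 658 in total. The point here does not depend on that. It takes accrual and sample size as the plan gives them.

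**Count of Table 1 items.** Patient 13 (Child-Pugh and MELD counted separately), imaging 4, intraoperative 8 (ablation duration counted per application and per tumor), postoperative 10, tumor 5, laboratory 12. Total 13 + 4 + 8 + 10 + 5 + 12 = 52. Multi-level factors such as surgeon or tumor location would need more than one column each. The patient, imaging, tumor and laboratory groups alone give 13 + 4 + 5 + 12 = 34.

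**Expected events.** Assume constant hazards and uniform entry.
- MWA alone: −ln(0.8)/2 = 0.1116 per year. MWA + TAE: −ln(0.9)/2 = 0.0527 per year.
- At 2 a month, median follow-up reaches 24 months at month 48, with 96 patients entered (48 per arm) and follow-up spread evenly over 0 to 4 years.
- Expected proportion with an event = 1 − (1 − S(4))/(4h).
- MWA alone: S(4) = 0.8² = 0.64, so 48 × [1 − 0.36/0.446] = 9.3.
- MWA + TAE: S(4) = 0.9² = 0.81, so 48 × [1 − 0.19/0.211] = 4.7.
- Total 14.0. With all 100 patients entered and a cut at month 50 it is 15.1. The 83-patient 2:1 option gives 10.9 to 12.2.

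Events per variable: 14.0/52 = 0.27 and 15.1/52 = 0.29. Loss to follow-up and censoring at transplantation would lower these.

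**Does a finite estimate exist?** Trials were simulated with these hazards and entry times and with mixed continuous and binary covariates. For each, a linear programme searched for a non-zero vector b with (xᵢ − xⱼ)′b ≥ 0 for every event i and every patient j still at risk, strict for at least one pair. If such a b exists, no finite maximum exists. Settings had 40 to 150 trials each; ranges are across runs with different covariate mixes.

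| Columns | Follow-up | Events | No finite estimate |
|---|---|---|---|
| 52 | median two years | 14–15 | 100% in every run |
| 40 | median two years | 14–15 | 84–99% |
| 34 | median two years | about 14 | 74–75% |
| 20 | median two years | 14–15 | 4–8% |
| 52 | last patient at 24 months (month 74) | 26–28 | 69–95% |
| 34 | month 74 | 26–28 | 0–2% |
| 52 | every patient 60 months | about 33 | 43–81% |

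The 52-column result did not change when the covariates were made prognostic or when 92 patients were used. Events per variable with longer follow-up are 27.6/52 = 0.53 and 33/52 = 0.63.

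**The case against.** The strongest reply is that the sentence does not say all variables, simultaneously. Table 1 also serves as the data-collection list, so the intention may have been one variable at a time, or a selection from the list. That reading is possible, but it is not the natural one: the text speaks of a single model and treats univariate analyses elsewhere with a different list. If selection was intended, its rule is missing.

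Second, the event count assumes intrahepatic disease-free survival at a median of two years. This model's endpoint is unnamed, 3- and 5-year outcomes are also planned, and no overall survival rate is given, so overall survival events cannot be computed. This stands and limits the point. Under assumed 2-year rates of 50% and 60%, about 40 events would be expected and only 7.5% of 50-column fits had no finite estimate, though events per variable would still be 40/50 = 0.8.

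Third, the analysis is exploratory. That lowers the priority but does not make the output interpretable.

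Two stronger inferences should be resisted. A reader might think that failure follows simply because variables outnumber events. It does not: 20 columns exceed 14 events yet rarely fail, and 34 columns mostly fail at month 48 but almost never at month 74. A reader might also suppose that correlated liver-function items make matters worse. The documents give no correlations, and in the one comparison at 34 columns a correlation of 0.5 gave 73% against 75% without it.

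**Conclusion.** The concern holds, conditionally. Read as one model for intrahepatic disease-free survival at the planned analysis, the Table 1 regression would have about 0.3 events per variable and, in simulation, essentially never a finite estimate. With longer follow-up a finite fit sometimes exists, but at 0.5 to 0.6 events per variable its hazard ratios and confidence intervals would still not be usable.

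This rests on the plan's own rates and accrual, constant hazards, uniform entry, and the single-model reading. A reader might infer that the plan commits the trial to an impossible fit in all circumstances, or that the main result is at risk. The documents support neither: the endpoint and timing of this model are left open, and the primary log-rank comparison does not use it. It should be corrected, but it is not a threat to the trial's principal conclusion.

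**What to change.** Replace the Table 1 sentence. State that:
- the multivariable Cox model is for intrahepatic disease-free survival and contains treatment arm plus a very small number of baseline variables (for example, at most two), named before any outcome data are seen;
- it is fitted with Firth's penalised partial likelihood and profile-likelihood confidence intervals, which the planned SAS software can do;
- the other baseline Table 1 variables are reported one at a time as description, without claims of significance;
- the expected number of events (about 14 to 15 at the planned analysis) is given beside the model and updated if the sample size changes.

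Two is a judgement, not a threshold: arm plus two single-parameter terms leaves 14/3 = 4.7 events per parameter, which is why the penalty is still needed. More terms could be considered if a revised sample size brought more events.

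The cost is a change of wording, with no new data, patients or procedures. The downside is that fewer adjusted hazard ratios are reported.

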Despite these suggested therapeutic benefits of combined thermal ablation and embolization techniques, little is known about the prognostic effects of MWA + TAE in early-stage HCC. To our knowledge, no RCTs have compared the combination therapy (MWA + TAE) with monotherapy (MWA alone) in this selective cohort. The efficacy of MWA in combination with TAE as a prophylactic treatment to reduce recurrence in HCC patients with a small tumor burden is unknown. Moreover, the optimal protocol and timing for MWA combined with TAE as a treatment for early stage HCC has yet to be determined. For all of these reasons, RCTs are required to examine the feasibility as well as the possible therapeutic and/or survival benefits of combination MWA + TAE in selected patients with early-stage HCC.

STUDY DESIGN

Objective

This single-center, prospective RCT is designed to compare the outcomes and clinicopathologic results of blunt transarterial embolization (TAE) and microwave ablation (MWA) combination therapy with MWA monotherapy for the treatment of early (stages 0 and A) hepatocellular carcinoma (HCC). The primary aim of this study is to test the following hypothesis: 2-year intrahepatic disease-free survival does not differ between patients receiving the experimental therapy (MWA + TAE) and patients receiving the standard therapy (MWA alone) as treatment for early-stage HCC. Secondary aims are: 1) to determine the clinical feasibility of TAE + MWA in HCC patients with a small tumor burden using patient demographics and disease characteristic data and 2) to determine the effect of TAE on radiographic tumor characteristics in this patient cohort.

The primary outcome is 2-year intrahepatic disease-free survival, which is measured from time of randomization and is defined as the absence of local or regional recurrence of HCC as determined by diagnostic imaging. *Local recurrence* is defined as an enhancing lesion contiguous with the ablation zone that is present on subsequent imaging but was not present on the initial postablation scan. *Regional recurrence* is defined as hepatic recurrence that is not adjacent to the ablation site.

Secondary outcome measures include:

- Patient and disease characteristics (Table 1)
- 1-year, 2-year, 3-year, and 5-year overall survival;
- 1-year, 3-year, and 5-year intrahepatic disease-free survival;
- Number of TAE procedures required (for multilobar lesions or repeat effect)

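### The plan calls every two-sided P value below .05 significant, including 26 univariate prognostic tests and the Table 1 Cox terms, with no limit on what that label may claim

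*Combined protocol and SAP*

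**What the plan says.** The last sentence of Statistical Analysis, which begins "All P values will be two-sided and a p value", sets .05 as the level below which any result is called significant. It is the only decision rule in that section. The Sample Size section plans the primary comparison at the same two-sided .05. The protocol gives no testing hierarchy, alpha allocation or multiplicity adjustment.

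The first paragraph of Statistical Analysis plans univariate tests of three groups of factors:

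- For the clinical group: "clinical variables (Child–Pugh class, Okuda class, Model for End-Stage Liver Disease (MELD) score, etiology of cirrhosis")
- For the tumor group: "tumor factors (extrahepatic disease, multicentric disease, tumor size, Milan criteria, AJCC tumor stage, AFP level")
- For the treatment group, with the two endpoints: "treatment-related factors (TAE, complications, recurrence) predicting intrahepatic disease-free and overall survival"

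That paragraph also names log-rank tests for survival and disease-free survival, by intention to treat. The last paragraph adds that "additional exploratory analyses will be performed to identify potential prognostic factors", using a Cox model on the Table 1 variables with hazard ratios and 95% CIs. Exploratory is applied expressly only to these additional analyses. The .05 rule follows in the same paragraph, so it covers them as well.

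Under Objective, a long list headed "Secondary outcome measures include" sets out outcomes and time points. For most of them no test is named anywhere.

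**The concern.** A significance label tells the reader that chance has been reasonably ruled out. When a single threshold is applied to a family of prognostic tests with no control across them, the label no longer means that for any one result. The reader cannot separate the one planned confirmatory comparison from a factor that happened to cross .05.

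The plan also states a use for the prognostic work: better selection of future patients. That purpose is attached to the additional exploratory analyses, but the rule would let even those be reported as significant. At stake is how prognostic and secondary findings are worded and then relied on.

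**Working it through.** The plan states no familywise error rate, so there is no figure of its own to reproduce. The input is the per-test threshold of .05 (Statistical Analysis).

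**Formulas.** For k independent tests with every null true, the chance of at least one P below .05 is 1 − 0.95^k. The expected number of false positives is 0.05 × k.

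**Step 1: tests named.** 4 clinical + 6 tumor + 3 treatment-related = 13 factors. On two endpoints this is 13 × 2 = 26 tests.

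**Step 2: remove tests that offer no separate chance of a false prognostic finding.**

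- TAE, 2 tests: these repeat the comparison between arms on each endpoint.
- Extrahepatic disease, 2 tests: apparently meant to be excluded at entry, although that exclusion criterion is awkwardly worded.
- Recurrence on intrahepatic disease-free survival, 1 test: local or regional recurrence is the event that defines the endpoint.

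26 − 2 − 2 − 1 = 21.

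**Step 3: remove factors where the null is doubtful on the documents' own account.** The Background lists the number and size of nodules and Child-Pugh class among prognostic variables. It also reports AFP as an independent predictor of local progression. Dropping Child-Pugh, multicentric disease and tumor size (3 × 2 = 6), AFP on disease-free survival (1) and, as a judgement, recurrence on overall survival (1) gives 21 − 8 = 13. Adding the overall survival log-rank between arms gives 14.

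| Set | k | At least one false positive | Expected |
|---|---|---|---|
| All named univariate tests | 26 | 1 − 0.95^26 = 73.6% | 1.30 |
| After step 2 | 21 | 1 − 0.95^21 = 65.9% | 1.05 |
| After step 3, with the OS log-rank | 14 | 1 − 0.95^14 = 51.2% | 0.70 |

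**Step 4: dependence.** The documents give no correlations, so these are assumptions.

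- The 21 tests are 10 factors on both endpoints plus recurrence on overall survival. If the 10 factors are independent and each factor's two tests correlate .8, simulation gives 55.6% for the 20 paired tests. Adding the last test as independent gives 1 − (1 − 0.556) × 0.95 = 57.8%.
- Under a common correlation of .3 / .5 / .7 among all tests, simulation gives 53% / 41% / 28% for 19 tests and 60% / 46% / 31% for 24, so 21 tests lie between. For 15 tests it gives 46% / 36% / 26%, and 14 tests lie slightly below.
- The expected counts in the table do not change with correlation.

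**Step 5: not counted.** Table 1 lists roughly 50 variables for the Cox model. Some repeat the univariate factors, and the plan does not say how many terms will be fitted, so no figure is attached to them.

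**The case against.** A trial with one primary endpoint does not need formal error control over secondary and prognostic analyses, and a nominal .05 is a common convention for them. This stands: the list leaves the primary comparison's type I error untouched, and a reader who inferred otherwise would be wrong. It limits the severity of the point. It does not justify using one label for both kinds of result.

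Several factors are plausibly real predictors, and others overlap (Child-Pugh, Okuda, MELD and AJCC stage measure related things). This stands too. It is why the 14-test figure is shown beside the 21, and why both probabilities are upper values under independence.

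The word additional could be read to mean that the univariate tests are exploratory as well. Even so, the .05 sentence speaks of all P values.

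A reader might go further and count the secondary outcomes as tests. By outcome and time point there are about 24, leaving out the ablation characteristics. Added to the 26, that makes 50 tests, a 92% chance of at least one false positive and 2.5 expected. The documents do not support this. The secondary items are outcome measures, and a test is named only for survival and disease-free survival. Seven of the 24 are time points on those two curves (four for overall survival, three for intrahepatic disease-free survival), and the log-rank test of intrahepatic disease-free survival is the primary comparison. Resection duration concerns only patients who go on to resection. The rule would cover any secondary comparison that is made, but how many will be made is not stated.

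Nor do the documents show that a chance secondary finding would become the trial's main message. That is a prediction about reporting, and the trial's power is a separate question.

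**Conclusion.** The point holds as a minor one. The plan states an explicit rule that lets any prognostic or secondary P value below .05 be called significant, without qualification and without control across the family. For the prognostic tests that it names, the chance of at least one false positive is 66% on 21 tests, or about even on 14. In numbers, roughly one or 0.7 false positives are expected.

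These figures assume that every null in the set is true, and the probabilities also assume independence. With positive correlation the probabilities fall, to below one half under a common correlation of .5. The set of 14 also rests on a judgement about recurrence and overall survival. The Table 1 Cox terms add to the exposure by an amount that cannot be fixed from the text.

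**What to change.** Replace the closing sentence of Statistical Analysis with a rule on these lines:

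- Only the primary log-rank comparison of intrahepatic disease-free survival may be called significant, at an overall two-sided .05. That level includes any efficacy test at the interim analysis, for which the plan gives no alpha rule.
- The overall survival log-rank and the other secondary outcomes are supportive.
- The univariate and Table 1 prognostic analyses are exploratory.
- Supportive and exploratory results are given as estimates with 95% CIs and nominal P values, without a claim of significance.

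This needs no extra patients, data or tests, and the plan already intends hazard ratios with 95% CIs for the Table 1 model. No formal adjustment of the prognostic tests is asked for. The cost is that the sponsor gives up the word significant for secondary and prognostic results, including the prespecified overall survival comparison. If an efficacy test is done at the interim analysis, its share of the .05 must also be stated in advance.
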